**Allocation method**

Individuals will be allocated by a stratified minimisation randomisation algorithm. Stratification variables will be the individual’s primary diagnosis (COPD/diabetes), and the baseline PRaDA risk of readmission in the following 12 months. The risk strata will consist of four evenly spaced risk sets (0.60-0.65, 0.65-0.70, 0.70-0.75, 0.75-0.80). The minimisation algorithm will be implemented within the study’s enrolment database.

Individuals agreeing to involvement in the study, and who are subsequently allocated, will be assigned a (sequential) allocation number; the combination of the screening number and the allocation number (for example, XXXXX-XXX) will give the unique individual study number. A master file containing individual UR, name, date of birth and study number will be stored separate to other study documents. This allocation and randomisation process will be guided and performed by [name] (Barwon Health Statistician\ Research Fellow)

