#### **Centre for Pattern Recognition and Data Analytics (PRaDA)**

Barwon Health has recently formed a partnership with Deakin University's, Centre for Pattern Recognition and Data Analytics (PRaDA). The Centre is currently analysing Barwon Health's hospital admission data and has ethical approval to do so. This type of analysis provides an innovative way to review, and identify, groups of consumers admitted to the acute hospital, as well as the likelihood of future admissions. A number of techniques utilised including detailed word association analysis. This enables Deakin University and Barwon Health professionals to understand the 'drivers' of anticipated hospital admissions. The availability of this data, and its associated analysis, will provide enhanced rigour in selecting a population that the Barwon Health Personalised Health Care model can test as a pre-emptive hospital avoidance model.

Using computer modelling the data analysis aims to expose latent patterns in health data and medical records, and assign individuals to these patterns. The method uses characteristics of individuals such as diagnosis, co morbidities, age, gender, admission & length-of-stay history, diagnosis procedures (rarity is also emphasised) past HbA1c measures, past operations and past medications to predict the likelihood of no admission to an acute hospital in the next 12 months. Based on the data analysis, a resultant likelihood of no admission between 0 and 1 can be assigned to a patient. This method has been performed on 2008-2010 Barwon health data with developers being blinded to 2011 data, which has then been used for validation. A paper describing this methodology and its accuracy is currently under review for publication at a peer reviewed journal. Figure 1 below shows the results of this analysis

Figure 1 Probability that a group of patients will NOT be readmitted in the next 12 months

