## **4. STUDY POPULATION**

### **Participant Identification**

Patients who meet the pre-set eligibility criteria as determined by medical consultants in the project team and the PRaDA *likelihood of no admission* parameters (refer to figure 1) set by the team will be eligible to participate in the pilot. See below for detail

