### **Selection Criteria**

#### *Inclusion criteria*

- Diagnoses of COPD or Diabetes (Type I and Type II)
- PRaDA “likelihood of admission in the next 12 months” value of 0.5-0.8
- Lives in own home

- Over 18 years of age
- Ability \ dexterity to enter and submit own data via a computer or similar device.
- English speaking or carer who is English speaking
- Willingness and ability to take own vital signs and biometric readings via appropriate selected device (e.g) a glucose meter or live with a carer who can.

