**Statistical analyses**

**Sample size**

This study is a pilot intended to gather information surrounding the efficacy and feasibility of the

intervention, and has not been powered to detect any (minimal) clinically relevant difference between the intervention and control arms. Sample size has been guided by available resources and funding.

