### **Methods**

Due to the pilot nature of the study, analysis of study data will not follow a hypothesis testing framework. Confidence intervals for efficacy outcomes will be calculated within each group at the 95% confidence level, however no formal significance tests will be made. Hospital admissions will be treated as a binary variable, ED presentations as counts, and LoS as ordinal. Total LoS (summed over all admissions) will be presented.

Allowances for stratification of the sample will be made via the Cochran–Mantel–Haenszel (CMH) test for unadjusted analyses, and adjustment for covariates will further be investigated via logistic regression for binary variables; adjustment for covariates will use Poisson regression for count variables. Analysis of the readmission rates will further be summarised under a time-to-event framework.

Baseline measures will be summarised by group, as will any differences post-intervention. Trial procedures (such as recruitment and retention rates, compliance and monitoring loads) will be monitored and summarised by confidence intervals where appropriate.

Following verbatim data transcription of each interview, a constant comparative thematic analysis method will be used. Two researchers will analysis the data independently and confer to confirm the thematic structure of the data.

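### The PRaDA risk strata for allocation start at 0.60, but patients are eligible from 0.50, so scores from 0.50 to below 0.60 have no stratum

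*Protocol*

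**What the plan says.** The inclusion criterion appears in identical words in the protocol synopsis and in Section 4 (Selection Criteria): "PRaDA “likelihood of admission in the next 12 months” value of 0.5-0.8".

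Section 10 (Allocation method) states that "Individuals will be allocated by a stratified minimisation randomisation algorithm". It names two factors: "Stratification variables will be the individual’s primary diagnosis (COPD/diabetes), and the baseline PRaDA risk of readmission in the following 12 months". It then lists the levels of the second: "The risk strata will consist of four evenly spaced risk sets (0.60-0.65, 0.65-0.70, 0.70-0.75, 0.75-0.80"). The algorithm is to be built into the enrolment database, and Section 10 (Participant numbers) places allocation at the time of consent.

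The analysis refers back to this design. Section 10 (Methods) says: "Allowances for stratification of the sample will be made via the Cochran–Mantel–Haenszel (CMH) test for unadjusted analyses".

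Elsewhere the score is described in the opposite direction. Section 1, in the account of the PRaDA centre, says that "a resultant likelihood of no admission between 0 and 1 can be assigned to a patient", and Section 4 (Participant Identification) also refers to a "likelihood of no admission".

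**The concern.** The list of risk sets is complete and stops at 0.60, while eligibility goes down to 0.50. A patient scoring 0.55 meets the criterion, signs consent and reaches the allocation step with no PRaDA level. Whoever programs or runs the database must then improvise: refuse the patient, force the score into the lowest set, or minimise on diagnosis alone. The first changes the study population from the one described. The other two depart from the stated scheme and weaken or lose the planned balance on a score built to predict admission, in a study where admission is itself an outcome.

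The same patients have no defined risk stratum when the unadjusted analysis allows for the stratification. The pilot is also meant to supply recruitment rates and outcome variability for a full trial, and both depend on who is enrolled.

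A smaller point sits in the same table: 0.65, 0.70 and 0.75 each belong to two adjacent sets.

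**Working it through.** **Inputs, all from the protocol**

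- Eligible range: 0.50 to 0.80 (synopsis; Section 4).
- Risk sets: 0.60–0.65, 0.65–0.70, 0.70–0.75, 0.75–0.80 (Section 10, Allocation method).
- Diagnosis: two levels (same section).
- Planned sample: 400, fixed by funding (Section 10), so there is no sample-size formula to reproduce.

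**The plan's own description.** Each set is 0.05 wide, so the claim of four evenly spaced sets is correct. Their total width is 4 × 0.05 = 0.20.

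**Comparison with eligibility**

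- Width of the eligible range: 0.80 − 0.50 = 0.30.
- Uncovered width: 0.30 − 0.20 = 0.10, from 0.50 to just below 0.60.
- Uncovered share of the range: 0.10 / 0.30 = 33.3%.

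**Patients affected.** The protocol gives no distribution of scores, so this can only be illustrated by assuming a share in the band:

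| Assumed share scoring 0.50 to <0.60 | Patients of 400 |
|---|---|
| 10% | 40 |
| 33% (uniform scores) | 133 |
| 50% | 200 |

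**Does the direction of the score explain the gap?** If a range is really a probability of no admission, the risk is one minus the score. The four combinations are:

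| Eligibility range is | Strata are | Eligible risk | Risk covered by strata | Result |
|---|---|---|---|---|
| admission | admission | 0.50–0.80 | 0.60–0.80 | lowest-risk third uncovered |
| no admission | no admission | 0.20–0.50 | 0.20–0.40 | highest-risk third uncovered |
| no admission | admission | 0.20–0.50 | 0.60–0.80 | no overlap |
| admission | no admission | 0.50–0.80 | 0.20–0.40 | no overlap |

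The first row is what the wording of the criterion and of the Allocation method says. No row closes the gap.

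**Strata that would fit 0.50–0.80**

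- Six sets of 0.05: 0.30 / 0.05 = 6. With diagnosis this makes 2 × 6 = 12 cells, against 2 × 4 = 8 now. The average cell size is 400 / 12 ≈ 33, against 400 / 8 = 50.
- Four sets of 0.30 / 4 = 0.075, with cut-points 0.50, 0.575, 0.65, 0.725 and 0.80. The number of cells stays at 8.

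**The case against.** The contradiction itself is hard to dispute, but its consequences can be overstated.

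- **Allocation is not strictly impossible.** A patient below 0.60 still has a diagnosis, and minimisation could run on that factor alone. This stands. The accurate statement is that the patient cannot be allocated by the stated rule, and the protocol does not provide for the alternative.
- **The link to the analysis is partly inferred.** The Methods section does not name the four sets, and the planned regressions could use the score as a continuous covariate. This also stands. However, diagnosis and PRaDA risk are the only stratification the protocol defines, so a CMH analysis that allows for it needs a stratum for every patient.
- **The count is assumption only.** The figure of 133 needs uniform scores; the true share could be smaller or larger. Only the one-third of the score range comes from the document.
- **The statistical harm is limited.** Without a PRaDA level, patients are subject to chance imbalance, which costs precision but does not bias the comparison. The study is a pilot with no power calculation and no formal significance tests. This is fair if patients are still randomised, but not if they are turned away, because that changes the population.
- **Shared end points are commonplace** and often settled in the database specification. Agreed: on their own they would be minor.

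**Conclusion.** The concern holds. Eligibility and the allocation strata contradict each other in current text, and the stated allocation rule fails for eligible patients with scores from 0.50 to below 0.60. This is a rule fixed wrongly in the protocol, not detail left for a later document.

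The size that rests on the document alone is one third of the eligible score range. Whether the uncovered band is the lowest-risk or the highest-risk part depends on the direction of the score, which the protocol leaves unsettled; the criterion as worded makes it the lowest. The document does not show whether 0.50 or 0.60 was intended as the lower limit. The point should be settled before allocation begins, because allocations already made cannot be redone.

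**What to change.** 1. State once whether the PRaDA score is a probability of admission or of no admission, and use that scale for both eligibility and strata.
2. Make the two ranges agree. Either:
   - keep 0.50–0.80 and extend the strata with half-open limits, as six sets ([0.50, 0.55), [0.55, 0.60), [0.60, 0.65), [0.65, 0.70), [0.70, 0.75), [0.75, 0.80]) or four sets ([0.50, 0.575), [0.575, 0.65), [0.65, 0.725), [0.725, 0.80]); or
   - if 0.60 was the intended floor, correct the inclusion criterion in the synopsis and in Section 4, and give the existing four sets half-open limits.
3. Program the enrolment database and the stratified analysis from the same table.

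Half-open limits also settle the scores that now fall in two sets. The four-set option keeps 8 diagnosis-by-risk cells; the six-set option makes 12, with about 33 patients in each on average.

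The cost is a protocol correction and one lookup table. No extra patients are needed, although a floor of 0.60 would narrow the pool of eligible patients relative to the criterion as now written.

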**Statistical analyses**

**Sample size**

This study is a pilot intended to gather information surrounding the efficacy and feasibility of the

intervention, and has not been powered to detect any (minimal) clinically relevant difference between the intervention and control arms. Sample size has been guided by available resources and funding.

### **Methods**

Due to the pilot nature of the study, analysis of study data will not follow a hypothesis testing framework. Confidence intervals for efficacy outcomes will be calculated within each group at the 95% confidence level, however no formal significance tests will be made. Hospital admissions will be treated as a binary variable, ED presentations as counts, and LoS as ordinal. Total LoS (summed over all admissions) will be presented.

Allowances for stratification of the sample will be made via the Cochran–Mantel–Haenszel (CMH) test for unadjusted analyses, and adjustment for covariates will further be investigated via logistic regression for binary variables; adjustment for covariates will use Poisson regression for count variables. Analysis of the readmission rates will further be summarised under a time-to-event framework.

Baseline measures will be summarised by group, as will any differences post-intervention. Trial procedures (such as recruitment and retention rates, compliance and monitoring loads) will be monitored and summarised by confidence intervals where appropriate.

Following verbatim data transcription of each interview, a constant comparative thematic analysis method will be used. Two researchers will analysis the data independently and confer to confirm the thematic structure of the data.

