### **Study Plan**

400 adults identified to be at a higher risk of readmission to hospital within the next 12 months who agree to participate will be randomised to either the intervention “usual care plus Personalised Health Care” group or the “usual care” control group. Patients in the intervention and control groups will be asked to participate for 12 months. Measures of hospital utilization and health literacy \ self-management will be measured at baseline and after 12 months of the intervention to determine if hospital utilization has decreased and if health literacy has increased for the intervention group.

*Usual Care control group* - Patient manages health condition as directed by usual and existing medical services, no limitations on care type that can be newly administered during the 12 months. Measures of Hospital Utilization, Health Literacy, self-management QOL at 0 and 12 months.

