#### *Usual Care plus “Personalised Health Care” Intervention group*

Telehealth patient monitoring with phone access to specialised nursing team, personalised escalation and care plans. Patient can still access all existing modes of care and emergency services. Measures of Hospital Utilization, Health Literacy, self-management QOL at 0 and 12 months.

Please also refer to Appendix A –Project Flow chart

In similar models of care operating, one nurse monitors approximately 100 patients. In line with this, our proposed service model aims to provide proof of concept for a service at this scale. The funding provided by the Department of health to operate the pilot model of care, is specified for 200 patients. Therefore the “intervention group” sample size will be a maximum of 200. The control group will also be 200 in order to monitor comparative changes.

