### **Intervention**

The intervention is an additional monitoring service on top of a patients “usual care”. There are three core aspects to the intervention; daily nurse monitored telehealth, personalised care plans and access to personalised advice from nurse team 24 hours a day which will provide a team of nurses and specialists the ability to respond early to the patient’s needs. Patients will have the ability to have contact with a nurse at any time. Research suggests that these aspects individually can improve the consumer’s understanding and ability to manage their own health conditions. This proof of concept pilot aims to demonstrate that a combination of these core aspects leads to decreased hospital utilisation as well as increases in health literacy and an improved ability to self-manage their health conditions.

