#### **5. RECRUITMENT**

All patients identified as meeting the selection criteria will be sent a letter regarding the pilot study with some information regarding the pilot study and what would be required of a participant. A reply paid envelope will be provided which includes preferred date, time and best method of contact; those interested to participate could indicate this and return to the research team. The program staff with administration support provided with this contact information (i.e. home, mobile phone, email). Responders interested in participation will be followed up by phone and an appointment arranged to meet and discuss the pilot study and their possible participation and appointment arranged if possible. Appointment reminders will be sent along with any pertinent information such as the PDCF prior to agreed time

Non-responders will also be followed up by sending a follow up invitation 2 weeks after the initial invite, The second invite will refer to the first and will highlight that there is a "not interested response" section. Any patient who chooses not to participate in the pilot at this stage will not be contacted again. Rolling enrolment will occur and over a period of 6 months. As patients are enrolled patients will be randomised to the control or intervention arms of the pilot. This gradual recruitment aims to recruit 200 individuals in the intervention group and 200 in the control group. Please see the statistical analyses section for detail on randomisation method

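### Efficacy intervals are fixed within each arm only; the protocol does not say that a between-arm effect will be reported with its interval

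*Protocol*

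**What the plan says.** The Methods text under Statistical analyses (protocol section 10) states that "analysis of study data will not follow a hypothesis testing framework". It continues: "Confidence intervals for efficacy outcomes will be calculated within each group at the 95% confidence level, however no formal significance tests will be made". Differences after the intervention are also to be summarised by group. Intervals are planned for trial procedures such as recruitment, retention and compliance, but these are not efficacy outcomes.

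The same text names methods that can compare arms. "Allowances for stratification of the sample will be made via the Cochran–Mantel–Haenszel (CMH) test for unadjusted analyses"; logistic regression is to be investigated for covariate adjustment of binary outcomes; Poisson regression will be used for adjustment of counts; readmission is also to be summarised as time to event. No risk difference, odds ratio, rate ratio or hazard ratio is named, and no interval for one.

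Elsewhere the protocol gives the control arm a comparative purpose: "The control group will also be 200 in order to monitor comparative changes" (Executive Summary, intervention group description; repeated in substance under Sample Size). The Study Plan in the Executive Summary says that measures at baseline and 12 months serve "to determine if hospital utilization has decreased and if health literacy has increased for the intervention group". The Intervention paragraph states a causal aim: "This proof of concept pilot aims to demonstrate that a combination of these core aspects leads to decreased hospital utilisation". The Sample size paragraph says that the study "has not been powered to detect any (minimal) clinically relevant difference between the intervention and control arms".

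**The concern.** The randomised contrast is the one quantity that the control arm makes available without bias from time trends or from the way patients were selected. The protocol does not leave its reporting open; it specifies intervals within each group. An analysis plan that followed this text literally would produce two arm-level intervals per outcome and no interval for the effect.

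Ruling out hypothesis tests does not explain the choice, because an interval for a difference or ratio requires no test. The one unadjusted between-arm procedure named is called a test, which conflicts with the statement that no formal significance tests will be made.

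The Study Plan clause adds to the problem because it can be read as a before-after question in the intervention arm. Eligibility depends on a PRaDA score that draws, among other things, on admission and length-of-stay history (section 1). Patients selected partly on past use may use less hospital care later whatever treatment they receive. A before-after reading could credit that fall to the program.

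At stake are the effect estimate and its precision, which a later, fully powered trial would want from this pilot.

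**Working it through.** **Inputs**

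- Sample size: "This gradual recruitment aims to recruit 200 individuals in the intervention group and 200 in the control group" (section 5).
- Admission is analysed as a binary outcome (Methods, section 10).
- Admission rate: not stated. I assume 50% to 80%, the eligibility range of the PRaDA score under Inclusion criteria, with 65% as the midpoint.
- Confidence level: 95%, as in Methods.

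There is no planned figure to reproduce. The total of 400 was set by funding, with no event rate, effect size or power behind it.

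**Formulas** (Wald, equal arms, common rate p)

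- Half-width within one arm: 1.96 × √(p(1−p)/200)
- Half-width for the difference: 1.96 × √(2p(1−p)/200), which is √2 times the first

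**Results**

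| Assumed p | Within one arm | Difference between arms |
|---|---|---|
| 0.50 | 1.96 × √(0.25/200) = ±6.9 points | ±9.8 points |
| 0.65 | 1.96 × √(0.2275/200) = ±6.6 points | ±9.35 points |
| 0.80 | 1.96 × √(0.16/200) = ±5.5 points | ±7.8 points |

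With 90% or 80% retention (also assumed) at p = 0.65, the interval for the difference widens to about ±9.9 or ±10.5 points.

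**What a reader of the two arm-level intervals would see**

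Take 65% admitted under usual care and 55% in the intervention arm, as an illustration.

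- Usual care: 65% ± 6.6, that is 58.4% to 71.6%.
- Intervention: 1.96 × √(0.55 × 0.45/200) = 6.9 points, that is 48.1% to 61.9%.
- The two intervals overlap.
- Difference: 10 points, half-width 1.96 × √((0.2275 + 0.2475)/200) = 9.55 points, so the 95% interval runs from 0.4 to 19.6 points.

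At p = 0.65 the arm intervals separate only when the gap exceeds 2 × 6.61 = 13.2 points. That is 2 × 1.96/√2 = 2.77 standard errors of the difference, or a two-sided level of about 0.006. Comparing arm intervals by eye is therefore much stricter than reading the 95% interval for the difference.

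**Regression to the mean**

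The documents give neither the distribution of prior use nor the link between prior use and the score, so its size cannot be computed.

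**The case against.** The strongest reply is that between-arm analysis is planned. The Cochran–Mantel–Haenszel method has an associated stratified estimator, logistic and Poisson models give odds and rate ratios with intervals, and Poisson adjustment for counts is stated firmly. The monitoring board is to watch the difference between groups, and the Publication Policy promises comparisons across groups. All of this stands. A reader might infer that the protocol has no between-arm analysis, and the text does not support that. What is missing is a statement that a between-arm estimate and its interval will be reported.

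A second reply is that the unadjusted interval can be recovered by combining the arms: √(6.6² + 6.6²) = 9.3 points. That is true for a simple difference of independent proportions. It does not give an estimate adjusted for the allocation factors or baseline. Within-arm summaries do serve the stated aim of assessing outcome variability.

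Three stronger readings are tempting and should be resisted:

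- *Success is defined as a before-after change.* The protocol has no success criterion. The before-after reading rests on one ambiguous clause in the Study Plan, both arms are measured at 0 and 12 months, and the control arm is there for comparison. The aim in the Intervention paragraph is causal and does not imply a before-after analysis.
- *The trial will judge by overlap of intervals.* No such rule is planned; the 0.006 level only describes what an informal comparison would amount to.
- *A particular fall in admissions would occur without treatment.* Selection is on a predicted risk built from many characteristics, and any figure would need parameters that the protocol does not give. Regression to the mean would affect both randomised arms, so a between-arm comparison deals with it.

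**Conclusion.** The point holds in a limited form. For efficacy outcomes the protocol specifies 95% intervals within each arm, does not commit to an interval for the randomised contrast, and names a test where it says that none will be made. The interval for the difference in admission is √2 times as wide as each arm's interval: about ±9.8 to ±7.8 points against ±6.9 to ±5.5. These figures rest on an assumed admission rate of 50% to 80%, equal rates in the arms, 200 per arm and full retention. The √2 ratio depends only on equal arm sizes and similar rates.

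This should be fixed but is not critical. The study is an unpowered pilot without tests or a success rule, and suitable models are already named.

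**What to change.** **In Methods (section 10).** For each efficacy outcome, state that a between-arm estimate with a 95% confidence interval will be reported, without a significance test. Adjust for the allocation factors (primary diagnosis and PRaDA risk) and for the baseline value where collected:

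- Admission: a Mantel–Haenszel risk difference or ratio, replacing the named test, with further adjustment through the logistic model.
- ED presentations: a rate ratio.
- Length of stay: an ordinal between-arm measure, in keeping with the scale that the protocol assigns.
- Time to readmission: a hazard ratio.
- AQoL and Health Education Impact Questionnaire: a mean difference at 12 months.

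Keep the within-arm summaries for the variability aim. Before pooling over strata, reconcile the risk strata, which start at 0.60 under Allocation method, with the eligibility range, which starts at 0.5; otherwise some eligible patients belong to no stratum.

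**In the Study Plan (Executive Summary).** Reword the sentence so that change in hospital use and health literacy is assessed as intervention versus control.

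**Cost.** Protocol and analysis-plan wording and a little more analysis. No new data are needed, and the decision not to test is preserved.

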**Data Storage/Record Retention**

Data	Pre and post measures of	Intervention	Control	Monitor only	Program Evaluation	Source
Length of Stay (LOS)	LOS or average LOS(s) at hospitalisation	✓	✓	✓	✗	Data Ware-House

Hospital Admissions	Number of hospitalisations in past 12 months	✓	✓	✓	✗	Data Ware-House	F v f c E f
ED Presentations	Number of ED presentations in past 12 months	✓	✓	✓	✗	Data Ware-House	F v f c E f
Quality of Life	Specific validated questionnaire	✓	✓	✗	✗		F v f c E f
Health Literacy \ Self management	Specific validated questionnaire	✓	✓	✗	✗		F v f c E f
Mortality		✓	✓	✓	✗	Hospital Data	F v f c E f
PRaDA	Predictive value of the patients (intervention vs control vs followed)	✓	✓	✓	✗	PRaDA	F v f c E f
Interviews	NA	✗	✗	✗	✓	Word files/PDF password	

						protected
--	--	--	--	--	--	-----------

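### The number of admissions per person is collected in both arms but analysed as any versus none; a count analysis should be added beside the binary one

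*Protocol*

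**What the plan says.** Protocol section 10, Methods, fixes the scale of each utilisation outcome: "Hospital admissions will be treated as a binary variable, ED presentations as counts, and LoS as ordinal". It assigns logistic regression to binary variables and Poisson regression to counts, so the choice of scale also settles the model. The same section promises total length of stay over all admissions, and a further time-to-event summary of readmission rates that does not say whether events after the first are used.

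The table under Data Storage/Record Retention lists "Number of hospitalisations in past 12 months" as a pre and post measure, ticked for both the intervention and control arms and drawn from the data warehouse. Section 2 lists acute admissions among the outcomes and makes outcome variability, for sizing a full trial, an aim of its own. The Executive Summary gives lower hospital utilisation as the purpose of the program.

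On the expected level of admissions, section 4 requires "PRaDA “likelihood of admission in the next 12 months” value of 0.5-0.8". The PRaDA description in section 1 says instead that "a resultant likelihood of no admission between 0 and 1 can be assigned to a patient", and Participant Identification in section 4 also refers to the likelihood of no admission. The Allocation method speaks of risk of readmission, with four bands from 0.60 to 0.80.

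**The concern.** Any/none scores one admission and five admissions alike. The more people who are admitted at least once, the more of the between-arm information lies in the second and later admissions, and this population is selected for a raised chance of admission. ED presentations, a parallel outcome from the same source, stay as counts, and no reason is given for the difference.

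Two things are at stake. One is precision on a main utilisation outcome, although the finer data are already in hand. The other is the pilot's planning role: a proportion admitted does not give the mean number of admissions or its overdispersion, and a later trial built on admission counts would need both.

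**Working it through.** There is no figure in the protocol to reproduce. The 200 per arm is set by funding, with no alpha, power or effect size.

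**Inputs from the protocol.** Range 0.5 to 0.8 (section 4, Inclusion criteria), read first as the probability *p* of at least one admission in 12 months. If it is read as the likelihood of no admission, *p* runs from 1 − 0.8 = 0.2 to 1 − 0.5 = 0.5.

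**Assumptions, not in the protocol.** Admissions follow a Poisson distribution, or a negative binomial with dispersion *k*; the program multiplies the rate by a common factor.

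**Poisson formula.** With mean *m* = −ln(1 − *p*), the information per person on ln *m* is *m* from the count and *m*²/(e^*m* − 1) from any/none. The relative efficiency is *m*/(e^*m* − 1) = *m*(1 − *p*)/*p*. The share of admissions beyond the first is 1 − *p*/*m*.

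| *p* | *m* | Efficiency of any/none | Loss | Share beyond first |
|---|---|---|---|---|
| 0.20 | 0.223 | 0.223 × 0.80/0.20 = 0.893 | 11% | 10% |
| 0.35 | 0.431 | 0.431 × 0.65/0.35 = 0.800 | 20% | 19% |
| 0.50 | 0.693 | 0.693 × 0.50/0.50 = 0.693 | 31% | 28% |
| 0.65 | 1.050 | 1.050 × 0.35/0.65 = 0.565 | 43% | 38% |
| 0.80 | 1.609 | 1.609 × 0.20/0.80 = 0.402 | 60% | 50% |

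The loss is therefore 31% to 60% if the range is the probability of admission and 11% to 31% if it is the likelihood of no admission. Over the allocation bands, 0.60 to 0.80 read as risk, it is 39% to 60%.

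**Interval width.** On the log-rate scale an interval widens by 1/√efficiency: 1/√0.693 = 1.20 at *p* = 0.5 and 1/√0.402 = 1.58 at *p* = 0.8. At *p* = 0.2 it is 1/√0.893 = 1.06.

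**Overdispersion.** For the negative binomial, P(0) = (1 + *km*)^(−1/*k*), count information is *m*/(1 + *km*), and any/none information is (d*p*/d ln *m*)²/[*p*(1 − *p*)]. Efficiencies at *p* = 0.5, 0.65 and 0.8 are 0.586, 0.440 and 0.276 for *k* = 0.5, and 0.500, 0.350 and 0.200 for *k* = 1. At *p* = 0.2 they are 0.845 and 0.800.

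**Planning value.** The same 65% admitted is compatible with a mean of 1.05 (*k* = 0), 1.38 (*k* = 0.5) or 1.86 (*k* = 1); any/none data cannot tell these apart. For illustration, take a rate ratio of 0.8, 80% power and two-sided 5%. The number per arm for a count-based trial is (1.96 + 0.842)² × [(1/*m* + *k*) + (1/(0.8*m*) + *k*)]/(ln 0.8)². This gives 338, 415 and 507 in the three cases.

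**The case against.** The case for leaving the plan alone has several sound parts.

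- **Any admission is a legitimate outcome.** It matches what the PRaDA score predicts and what patients are selected and stratified on. It is not swayed by a few very frequent attenders. It answers a different question from the rate, so efficiency for a rate ratio is not the only criterion. This stands, and is why the binary outcome should stay.
- **The trial makes no power claim.** It "has not been powered to detect any (minimal) clinically relevant difference between the intervention and control arms", and "Confidence intervals for efficacy outcomes will be calculated within each group at the 95% confidence level, however no formal significance tests will be made". This stands too. A reader might infer that the binary coding leaves the pilot underpowered; the protocol does not support that, because no power was claimed.
- **Repeat admissions are not absent.** A reader might infer that the plan misses them altogether. Total length of stay picks them up in part, though mixed with the duration of each stay. The time-to-event summary may use recurrent events, and that detail can properly sit in a statistical analysis plan.
- **A descriptive mean and SD of the count are not ruled out.** Methods promises group summaries of baseline measures and of post-intervention differences. So it would be too strong to say that the pilot cannot estimate the mean and variance; the point is that no such estimate is stated.

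What remains is that Methods makes a positive choice of scale for this outcome, and the choice leaves the collected count without a stated analysis.

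**Conclusion.** The point holds as a gap in a stated analysis choice. Under a Poisson model and a common rate ratio, any/none gives up about 31% to 60% of the information on the log rate ratio if 0.5 to 0.8 is the probability of admission, and more with overdispersion. If that range is the likelihood of no admission, the loss is about 11% to 31%.

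A reader might sum this up as about half the information discarded. That fits only the middle of the first reading, and it rests on an assumed count distribution and a score direction on which the protocol contradicts itself. The inclusion criterion and the allocation bands favour the first reading; the PRaDA description and Participant Identification favour the second.

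On either reading the consequence is a wider interval on one utilisation outcome, and no stated estimate of the admission rate and its overdispersion for the later trial.

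**What to change.** In section 10, Methods, add the number of acute admissions per participant over 12 months as a count outcome alongside the binary one. Analyse it with a model that allows for overdispersion (negative binomial, or Poisson with robust variance), with a log follow-up-time offset and adjustment for the stratification variables. Report the rate ratio with its 95% confidence interval, and the mean and variance of the count by arm. Keep any admission and the time-to-event summary.

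Separately, reconcile the direction of the PRaDA score between section 1, Participant Identification, the inclusion criterion and the allocation bands.

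The cost is one more analysis and a change of wording, since the counts are already collected. A rate ratio is slightly less direct to explain than a proportion.
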